2.3 Visit Structure

The visit structure and scheduled assessments are detailed in Section 5.2 and Appendix 1 in the study protocols.

2.4 Sample Size

As stated in Introduction the dosing of IMP stopped earlier than planned. Hence, the sample size assumptions originally stated in the protocols do not longer hold. In POLAR-A a total of n=301 patients have been randomised as compared to the planned n=280, and in POLAR-M n=290 patients have been randomised as compared to the planned n=420. The sample size protocol text below are stated for reference.

Protocol text (Section 10.2 in the CSPs)

The assumption of the proportion of patients who will satisfy the criteria for the primary endpoint in the untreated (placebo) study population is based on the results in the SCOT trial. Results were presented at ASCO 2017 and roughly 40% of the placebo population had symptoms graded “quite a bit/very much”, which corresponds to 3 or more in this study.

With 112 patients per group, the **POLAR-A** study has 91% power to detect a reduction (improvement) from 40% to 20% (OR = 0.375) in the primary endpoint using two-sided test controlled at the 0.05 type-I error rate. To account for 20% dropout in the study, in total 280 patients (140 patients per arm) will be randomised.

With 112 patients per group, the **POLAR-M** study has 91% power to detect a reduction (improvement) from 40% to 20% (odds ratio = 0.375) in the primary endpoint using two-sided test controlled at the 0.05 type-I error rate. To account for 20% dropout in the study, in total 420 patients (140 patients per arm) will be randomised.

Sample size assumptions will be monitored in a blinded fashion as part of the regular monitoring of the study. In case there are indications these are not met; a re-estimation of the sample size may occur.

2.5 Changes From the Protocol Planned Analysis

Premature stop of administration of IMP in both POLAR-A and POLAR-M as well as the premature stop of recruitment in POLAR-M has several implications for the statistical analyses and the evaluation of the study data:

- Primary analysis. The Cochran-Mantel-Haenszel method described in the protocols has been fully specified to also include adjustment for cumulative oxaliplatin exposure. This amounts to replacing N, the number of subjects, in the divisor of the event rate calculation with cumulative oxaliplatin exposure. Also, in the protocols the CMH approach also adjust for FACT/GOG at baseline, but since there were very few patients with CIPN at baseline the primary analysis described in Section 5.1.1. does not include FACT/GOG at baseline.
- A negative binomial model will also be applied to the primary endpoint data as a supportive or exploratory analysis.
- Earlier stop of recruitment in POLAR-M has resulted in actual n=290 randomised patients as compared to the planned n=420.
- The primary analysis will be on the combined dataset including both POLAR-A and POLAR-M where study will be used as a stratification factor in all statistical analyses. Both studies will also be reported separately (see details in Section 3).
- Due to the lack of exposure of IMP a modified ITT (mITT) analysis set has been defined that will replace the Full Analysis Set (FAS). See further details in Section 3.1.
- Statistical analyses and summary tables will include data up to 12 months after the first dose of IMP (Assessment Visit 4). Data that has been collected after Assessment Visit 4 will only be included in the listings by patient.

Miscellaneous changes from the protocol planned analyses:

- The endpoint “mean health index using the FACT/GOG” as stated in the protocols will not be analysed.
- The variable Body Temperature although specified in vital signs section of the protocol has not been collected in the studies.
- In the CSP it says “PledOx Toxicities” but has been re-defined here in the SAP as “IMP Toxicities” since that is the way the data is collected and reported.

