2. STUDY OBJECTIVES AND DESIGN

2.1 POLAR-A

2.1.1 Primary Objective

The primary objective of the study is to compare PledOx (5 $\mu\text{mol/kg}$) vs placebo with respect to the proportion of patients with moderate or severe chronic CIPN.

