3.2 Hypothesis to be Tested

With respect to the primary endpoint Moderate to Severe CIPN at 9 months after first dose of IMP the statistical hypothesis to test is:

$$H_0: \mu_{5\mu\text{mol/kg}} = \mu_{\text{placebo}}$$

$$H_1: \mu_{5\mu\text{mol/kg}} \neq \mu_{\text{placebo}}$$

where μ_x represents the oxaliplatin-dose adjusted Moderate to Severe CIPN event rate at 9 months on treatment x . The treatment effect will be captured as the ratio of event rates, $\Psi = \mu_{5\mu\text{mol/kg}} / \mu_{\text{placebo}}$, so that the preceding null and alternative hypotheses can be reframed as

$$H_0: \Psi = 1 \text{ versus } H_1: \Psi \neq 1$$

A rate ratio <1 favours the PledOx 5µmol/kg group over placebo.

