5.1 Primary Endpoint

5.1.1 Moderate to Severe CIPN

The primary endpoint is defined as the proportion of patients (with moderate or severe chronic CIPN) scoring 3 or 4 in at least 1 of the first 4 items of the FACT/GOG-NTX-13 (i.e., FACT/GOG-NTX-4), targeting numbness, tingling or discomfort in hands and/or feet, 9 months after the first dose of IMP (i.e. PledOx or placebo administered on Day 1, Cycle 1 of mFOLFOX6 chemotherapy).

Baseline is defined as the time of administration of the first dose of IMP (Day 1, Cycle 1).

Moderate to Severe CIPN will derived (SAS) as follows:

```
cipn=0;  
IF ntx1_std=. AND ntx2_std=. AND ntx3_std=. AND ntx4_std=. THEN cipn=.;  
ELSE IF ntx1_std IN('3','4') OR ntx2_std IN('3','4') OR  
      ntx3_std IN('3','4') OR ntx4_std IN('3','4') THEN cipn=1;
```

Primary Analysis – Cochran-Mantel-Haenszel. The primary analysis of the primary endpoint Moderate to Severe CIPN (yes/no) at 9 months after first dose of IMP will be analysed by the Cochran-Mantel-Haenszel (CMH) estimate of the common relative risk of Moderate to Severe CIPN. The treatment effect will be assessed by estimating the ratio of the incidence rates of CIPN in PledOx 5µmol/kg versus Placebo along with its 95% confidence interval and corresponding p-value. The CMH estimate will be adjusted for cumulative exposure of oxaliplatin and stratified by study and region. Incidence rates (95% CIs) for each treatment will also be presented.

Notations. The combined analysis includes two studies (POLAR-A and POLAR-M) and two geographical regions (Asia/Non-Asia), and so there are 4 strata, where

- 1 = POLAR-A / Asia
- 2 = POLAR-A / Non-Asia
- 3 = POLAR-M / Asia
- 4 = POLAR-M / Non-Asia

Treatments are denoted by 1 and 2, where 1 = PledOx 5µmol/kg and 2 = Placebo. For treatment j in the i^{th} strata the cumulative exposure of oxaliplatin is T_{ij} and E_{ij} is CIPN events. Let $T_{i\bullet} = T_{i1} + T_{i2}$ and $E_{i\bullet} = E_{i1} + E_{i2}$ denote total cumulative exposure of oxaliplatin and total CIPN events in the i^{th} strata.

CMH point estimate of the common relative risk across strata. Under $H_0: R_1 = R_2 = R$, Breslow and Day [1] provide the stratified Cochran-Mantel-Haenszel estimate of the common relative risk as

$$\hat{R}_{M-H} = \frac{\sum_{i=1}^k \frac{E_{i1}T_{i2}}{T_{i\bullet}}}{\sum_{i=1}^k \frac{E_{i2}T_{i1}}{T_{i\bullet}}}$$

Also, Robins, Breslow and Greenland [2] provide an estimate of the variance of $\log \hat{R}_{M-H}$ as

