Supportive Analysis of the primary endpoint - Negative Binomial Regression. A supportive analysis of the primary endpoint Moderate to Severe CIPN (yes/no) at 9 months after first dose of IMP will be analysed by a negative binomial regression model adjusted for study (POLAR-A / POLAR-M) and region (Asia / non-Asia). An offset variable will also be used to adjust for the oxaliplatin exposure defined as the logarithm of the cumulative dose of oxaliplatin received by each patient. Estimate of the treatment contrast (rate ratio) and its corresponding 95% confidence interval will be based on the anti-log of the model parameter estimate and CI.

SAS Code Example Negative Binomial Regression using PROC GENMOD

```
PROC GENMOD;
  CLASS study region trt;
  MODEL cipn = study region trt/DIST=negbin LINK=log SCALE=deviance OFFSET=log_exp;
  ESTIMATE 'PledOx 5 µmol/kg vs Placebo' trt 1 -1;
  LSMEANS trt / CL EXP;
RUN;
```

If convergence criterion is not met using PROC GENMOD an alternative using PROC NLMIXED will be used.

SAS Code Example Negative Binomial Regression using PROC NLMIXED

```
PROC NLMIXED;
  PARMs b0 -2 b1 .1 b2 -.01 b3 .1 phi .1;
  eta = log_exp + b0 + b1*(study=1) + b2*(region=1) + b3*(trt=0);
  mu = exp(eta);
  LL = y*log(phi*mu) - (y+(1/phi))*log(1+(phi*mu)) + lgamma(y+(1/phi)) -
lgamma(1/phi) - lgamma(y+1);
  MODEL y ~ general(LL);
RUN;
```

Exploratory Analysis – Exact Logistic Regression. An exploratory analysis of the primary endpoint Moderate to Severe CIPN at 9 months after first dose of IMP will be analysed by exact logistic regression model adjusted for study (POLAR-A / POLAR-M) and region (Asia / non-Asia). Estimate of the treatment effect and its corresponding 95% confidence interval will be based on the odds-ratio.

SAS Code Example Exact Logistic Regression

```
PROC LOGISTIC DESC;
  CLASS study region trt(ref='0: Placebo');
  MODEL cipn = study region trt;
  EXACT trt;
RUN;
```

Using the same example data presented above, a crude estimate of the odds-ratio then is:

$$(0.27/0.73) / (0.41/0.59) = 0.53$$

Table 4 Example data: Exact Logistic Regression of Moderate to severe CIPN 9 months after first dose of IMP

	N	CIPN (%)	Odds-ratio	95% CI	P-value
PledOx 5 µmol/kg	118	27.1	-	-	-
Placebo	118	40.7	-	-	-
PledOx 5 µmol/kg vs Placebo	236	-	0.54	[0.31;0.94]	0.0293

Data Presentations

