5.3.3 Cumulative Dose of Oxaliplatin

Mean cumulative dose of oxaliplatin administered per patient during mFOLFOX6 chemotherapy, 9 months after the first dose of IMP. Summary statistics of oxaliplatin related variables are presented in Section 4.4.2.

In case the patient receives more than 12 cycles of oxaliplatin, that will also be accounted for when deriving the cumulative dose.

Analysis of Variance. Mean cumulative dose of oxaliplatin will be analysed by Analysis of Variance (ANOVA) using study (POLAR-A / POLAR-M), region (Asia / non-Asia) and treatment as factors. Least square means and its corresponding 95% confidence intervals will be presented.

Data presentation

- Table: ANCOVA analysis - Number of patients (N), Point Estimate (LSM), 95% CI and P-value by treatment group/treatment comparison (PledOx 5 µmol/kg vs Placebo).

All observed values of mean cumulative dose of oxaliplatin will also be listed by patient.

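### The primary test compares CIPN events per unit of oxaliplatin, not the proportion of patients with CIPN, and its divisor is a post-randomisation secondary endpoint

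*SAP*

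**What the plan says.** Section 2.1.1 sets the POLAR-A objective as a comparison of PledOx with placebo "with respect to the proportion of patients with moderate or severe chronic CIPN". Section 2.2.1 does the same for each dose in POLAR-M. Section 5.1.1 agrees: "The primary endpoint is defined as the proportion of patients (with moderate or severe chronic CIPN) scoring 3 or 4 in at least 1" (that is, one or more among four FACT/GOG-NTX items), measured 9 months after the first dose of IMP.

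The analysis is on another scale. Section 2.5 says of the modified Cochran-Mantel-Haenszel method: "This amounts to replacing N, the number of subjects, in the divisor of the event rate calculation with cumulative oxaliplatin exposure". In Section 3.2 the parameter under test "represents the oxaliplatin-dose adjusted Moderate to Severe CIPN event rate at 9 months on treatment", and the null hypothesis is that the ratio of these rates is 1. In the formulas of Section 5.1.1, E_ij is the number of events and T_ij the cumulative oxaliplatin exposure of arm j in stratum i. The same section gives the unit as events per unit dose.

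Cumulative oxaliplatin dose is also a secondary efficacy objective (Sections 2.1.2 and 2.2.2) and a secondary endpoint compared between arms by ANOVA (Section 5.3.3).

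The supportive negative binomial model uses the logarithm of the same dose as an offset. The only between-arm test of the primary endpoint that does not involve dose is the exact logistic regression, which is labelled exploratory.

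**The concern.** The objective asks whether fewer patients have CIPN. The test asks whether there are fewer events per milligram of oxaliplatin. The answers can differ whenever the arms receive different amounts of oxaliplatin. The plan treats that as an open question, since it compares dose between arms as an efficacy endpoint.

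This is not patient-level adjustment for dose. Only arm totals within each stratum enter the formula, so the arm's mean dose acts as a plain multiplier on the risk ratio. If the CIPN proportions are equal but the doses differ, the null hypothesis of Section 3.2 is false. Rejecting it does not establish the objective. Conversely, a real reduction in the proportion can be masked if PledOx patients receive less oxaliplatin.

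Section 2.5 attributes the changes to the early stop of IMP and of POLAR-M recruitment. It does not say why lost IMP exposure calls for oxaliplatin as the divisor.

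**Working it through.** **Identity.** Within a stratum, let p be the proportion with CIPN, d the mean oxaliplatin dose and n the number of patients in an arm (1 = PledOx, 2 = placebo). Then E = n·p and T = n·d, so

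R = (E1/T1)/(E2/T2) = (p1/p2) × (d2/d1).

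The strata are then pooled with Mantel-Haenszel weights. Write r = d1/d2.

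**Variance.** With one stratum, the SAP's variance of log R reduces to 1/E1 + 1/E2. It does not depend on dose.

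**Reproducing the SAP's Table 3.** Table 2 has 32 and 48 events among 118 patients per arm. The printed rates imply T1 = 32/0.000317 = 100,946 and T2 = 48/0.000462 = 103,896. These are means of about 855 and 880 mg/m² per patient, so r is about 0.97. SE = √(1/32 + 1/48) = 0.2282. The formula gives R = 0.686 (0.439 to 1.073), p = 0.099. The SAP prints 0.6869 (0.4391 to 1.0745), p = 0.0999, so the table is reproduced within rounding.

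**Same CIPN counts, different dose ratio.** R = (32/48)/r, with SE 0.2282 throughout:

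| r (assumed) | R | p |
|---|---|---|
| 0.90 | 0.741 | 0.189 |
| 1.00 | 0.667 | 0.076 |
| 1.05 | 0.635 | 0.047 |
| 1.10 | 0.606 | 0.028 |

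Significance requires R < exp(−1.96 × 0.2282) = 0.639, that is r > 0.6667/0.639 = 1.043.

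**Equal proportions.** If p1 = p2, then R = 1/r: 1.11, 0.91 and 0.83 at r = 0.90, 1.10 and 1.20.

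**Simulation.** SAP estimator and variance, 40,000 trials per case. Assumed: 200 patients per arm and a coefficient of variation of dose of 0.3. Benefit is declared if z < −1.96, for which the nominal rate is 2.5%. With 40% CIPN in both arms:

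| Strata (patients per arm) | r = 1.00 | 1.05 | 1.10 | 1.20 |
|---|---|---|---|---|
| One | 0.66% | 1.85% | 4.44% | 15.3% |
| 30/120/15/35 | 0.72% | 1.77% | 4.44% | 15.4% |
| 50 × 4 | 0.72% | 1.94% | 4.36% | 15.5% |

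Stratification changes nothing material. The rate at r = 1.00 lies below 2.5% because the variance is of Poisson type while each patient can have at most one event.

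**Masking.** With true proportions of 40% and 27% and one stratum, a significant benefit is found in 63.1% of trials at r = 1.00 and 34.7% at r = 0.90.

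**What the divisor explains, and what it does not.** On the example counts, p is 0.0999 as printed, 0.076 with patients as divisor and the Poisson-type variance kept, and 0.031 with patients as divisor and binomial variance (risk ratio 0.667, 95% CI 0.462 to 0.963). Only the first step is due to the divisor. The second is a separate matter of variance.

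**The case against.** The strongest defence is that this is a declared choice of estimand. Section 2.5 announces it, Section 3.2 states the hypothesis on that scale, and Section 5.1.1 gives the matching estimator and unit. On that view, equal CIPN after more of the drug that causes it is a real per-dose difference, and rejection in the equal-proportion scenario is power, not error. That is correct for the hypothesis as written in Section 3.2, but that hypothesis is not the stated objective. Rewording the objective and endpoint would remove the contradiction. The conclusion would still rest on a post-randomisation divisor and would no longer say how many patients are spared CIPN.

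The second argument is size. The rate of declared benefit stays below 2.5% until r is about 1.06 to 1.07 (2.2% and 2.7%). With a dose CV of 0.3 and 200 per arm, the chance SD of r is about 0.3 × √(2/200) = 0.03, so a ratio of 1.10 needs a real effect of treatment on dose delivery. The only ratio that the SAP implies, 0.97 in its invented example, moves the result slightly against PledOx. All of this stands as context. The low rate near r = 1 comes from the conservative variance, however, and does not cure the mismatch.

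Third, a dose-driven result would be visible: CIPN proportions by arm with exact intervals, the odds ratio and oxaliplatin dose by arm are all reported. That helps a reader interpret the result, but the formal conclusion still comes from the per-dose test.

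**Conclusion.** The concern holds. The primary hypothesis and test are on events per unit of oxaliplatin, the objective and endpoint are a proportion of patients, and the divisor is a post-randomisation outcome that the plan itself analyses as efficacy. A significant primary result would not by itself show that fewer patients have CIPN.

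The mismatch and the identity follow from the text and need no assumption. The size does: it rests on assumed dose ratios, 200 patients per arm and a dose CV of 0.3. The direction cannot be known in advance. More oxaliplatin on PledOx favours it and less works against it. A 4% difference in mean dose in PledOx's favour is enough to turn the SAP's example counts from p = 0.076 at equal dose to significance. Because the change is disclosed and the actual dose ratio is unknown, this should be changed, but it is not a concealed departure.

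**What to change.** Before unblinding:

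- Make the primary analysis the Mantel-Haenszel risk ratio stratified by study and region, with the number of patients as divisor and the binomial variance that belongs with it.
- Restate Section 3.2 in terms of proportions.
- Keep the oxaliplatin-divided rate ratio as a supportive analysis beside the negative binomial model.
- State which version applies where other parts rely on the method of Section 5.1.1: the POLAR-A test in Section 3, the tipping point analysis in Section 5.2, and the endpoints in Sections 5.3.1 and 5.3.7.

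This is not a full return to the protocol's analysis, which according to Section 2.5 also adjusted for baseline FACT/GOG. The SAP's reason for dropping that adjustment, very few patients with CIPN at baseline, can stand.

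The cost is SAP wording and the corresponding output shells; no new data are needed. The one loss is that the primary result no longer describes protection per unit of oxaliplatin. That remains available in the supportive analyses.

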3. GENERAL STATISTICAL PRINCIPLES

Testing Procedure. The formal testing procedure of the primary endpoint is first to perform the analysis on PledOx 5 µmol/kg vs Placebo on both POLAR-A and POLAR-M studies combined. If the results are statistically significant then the same analysis will be performed on the POLAR-A study alone. All tests will be done on the 0.05 level of significance.

Statistical analyses will include stratification factors for study (POLAR-A / POLAR-M) and region (Asia/non-Asia).

3.1 Analysis Sets

The analysis set “All randomised patients (ITT)” consists of all patients who were assigned a randomisation number, irrespective of the treatment they received, if any.

The modified ITT (mITT) analysis set includes patients that fulfil at least one of the following criteria:

1. the patient was randomised prior to December 1, 2019 (ie the patient was eligible for at least 3 months of IMP) and had at least one post-baseline assessment for efficacy, or
2. the 3 month Assessment Visit occurred prior to 1 March, 2020, or
3. the patient received the 6th cycle of IMP after 1 March, 2020.

Patients will be analysed according to the treatment they are assigned to at randomisation, irrespective of what treatment they actually received.

The safety analysis set (SAF) consists of all randomised patients who receive at least one dose of IMP. Patients will be analysed according to the randomised study treatment actually received.

The list of patients to be included in each of the analysis sets is to be agreed between the project statistician and the Sponsor prior to unblinding, once all study data is available.

All enrolled patients will be listed indicating their membership to each analysis set along with the reason for exclusion.

The PK population (POLAR-M only) includes a subset of patients at pre-selected sites in all participating regions, where blood samples will be collected for pharmacokinetics and ECG assessments.

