1. INTRODUCTION

The pivotal Phase 3 POLAR program, studying calmagafodipir for the prevention of chemotherapy induced peripheral neuropathy, consists of two studies: POLAR-A and POLAR-M.

- POLAR-A is a placebo controlled, randomised (1:1) Phase III study of calmagafodipir 5 µmol/kg in combination with mFOLFOX6 compared to placebo+mFOLFOX6 in patients with adjuvant treatment of stage III or high-risk stage II colorectal cancer.
- POLAR-M is a placebo controlled, randomised (1:1:1) Phase III study of calmagafodipir in two different doses, 2 µmol/kg and 5 µmol/kg in combination with mFOLFOX6 compared to placebo+mFOLFOX6 in patients with metastatic CRC.

Patient recruitment in the POLAR-A and POLAR-M studies was initiated in late 2018 with the first patient randomised in on January 15, 2019, in POLAR-A and on POLAR-M on January 21, 2019.

On January 23, 2020, the Sponsor announced that the US Food and Drug Administration (FDA) had issued a clinical hold in the US of the POLAR program. The implication was that recruitment and dosing of patients in the POLAR-M study was halted in the US. Based on the evaluation of the independent Drug Safety Monitoring Board (DSMB), the Sponsor's position was that the overall safety profile for PledOx supported the continuation of the POLAR program and both studies continued as planned in Europe and Asia with dosing and further recruitment.

On March 1, 2020, the Sponsor decided to place recruitment and dosing of patients in the POLAR program on hold. The decision followed interactions with the French regulatory authority, ANSM, and the clinical hold issued by the US Food and Drug Administration (FDA) earlier in the year and was due to 4 observed events related to seizure. The Sponsor maintained its position that these events are not related to calmagafodipir, a position which was also supported by the DSMB and an additional independent external evaluation of these cases.

On April 6, 2020, the Sponsor decided to close the POLAR program early with a data cut-off targeted for the third quarter 2020 (further detailed later in this document). The decision was taken after a recommendation from the DSMB to stop the studies due to an accumulation of severe allergic reactions, primarily observed after repeated dosing.

Based on the development of the POLAR studies, a re-assessment of the sample size assumptions is needed to determine a reasonable statistical approach to the analysis of the POLAR studies.

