The POLAR studies were designed based on the following sample size assumptions:

- POLAR-A: With 112 patients per group, the POLAR-A study has 91% power to detect a reduction (improvement) from 40% to 20% (OR = 0.375) in the primary endpoint using two-sided test controlled at the 0.05 type-I error rate. To account for 20% dropout in the study, in total 280 patients (140 patients per arm) will be randomised.
- POLAR-M: With 112 patients per group, the POLAR-M study has 91% power to detect a reduction (improvement) from 40% to 20% (odds ratio = 0.375) in the primary endpoint using two-sided test controlled at the 0.05 type-I error rate. To account for 20% dropout in the study, in total 420 patients (140 patients per arm) will be randomised.

Table 1: Patient disposition in the POLAR studies

	POLAR-A	POLAR-M	Total
Number of patients randomised	301	290	591
Number of patients dosed with ≥ 1 cycle of IMP	297	285	582
Number of patients dosed with ≥ 6 cycles of IMP	257	194	451
Number of patients dosed with ≥ 12 cycles of IMP	107	98	205

A total of 591 patients was randomised in the POLAR program and 582 patients dosed, of which 451 patients completed 6 cycles and 205 patients completed 12 cycles (see Table 1).

There are two main contributing factors to take into account when designing a reasonable statistical approach to the analysis of the POLAR studies:

- 1) POLAR-M only randomised 290 out of the planned 420 patients. This, together with the reduced dosing of patients (see bullet 2 below) means a separate primary analysis based on this data set cannot be supported.
- 2) Due to the Sponsor's decision to place the dosing of patients on hold on March 1, 2020, not all patients have had sufficient dosing of IMP to expect the full treatment effect of active treatment as assumed in the sample size calculation.

Taking these two aspects into consideration account (the fewer number of randomised patients and the reduced dosing of patients) a reasonable statistical approach is to conduct a combined primary analysis across the two studies, with the data from the two studies regarded as strata, based on a modified ITT analysis set defined by the eligibility of dosing with IMP as intended in the clinical study protocol. In addition, a standalone analysis of the primary endpoint in the fully recruited POLAR-A study will be conducted if the combined analysis is statistically significant. This approach will be further detailed in this document.

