5. EFFICACY EVALUATION

Unless otherwise stated, all efficacy variables will be analysed using the MITT analysis set. The general principles for handling unscheduled or repeated measurements is described in Section 3.4.

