5.2 Handling of Missing Data in the Primary Endpoint

For the primary endpoint Moderate to Severe CIPN (yes/no) the following methods of imputation will be used for the primary analysis in case of missing:

1. Observed cases (no imputation)
2. “Non-responder” if missing (ie 3 or 4 on FACT/GOG)
3. Tipping point analysis – combinations of missing data values that would change the conclusion. References eg Yan (2009), Rubin (2012)

A tipping point analysis assesses the potential impact of informative missingness by progressively penalizing patients with missing data in the experimental arm. The goal is to find the level of penalization that results in loss of statistical significance on the primary endpoint.

The steps to perform the tipping point analysis are as follows:

1. The NB model as described in Section 5.1.1 is applied to each randomised treatment arm separately based on the observed data in that arm. This will give two parameters for each of the experimental and control groups, the event rate, μ , and the dispersion rate, κ .
2. For each subject, i , in the experimental arm who had $t_i < 9$ months follow-up and who did not record a primary endpoint event in the period $(0 - t_i]$, simulate their event rate, μ_i , by randomly sampling an observation from a $Gamma(shape = 1/\kappa, scale = 1/(\kappa\mu))$ distribution.
3. Using μ_i , the time to event for subject i in the period $(t_i, 9]$ is given by $\Delta_i = -\ln(1 - \omega_i)/\mu_i$ where ω_i is a random deviate from a $U(0,1)$ distribution.
4. If $t_i + \Delta_i \leq 9$ then subject i is considered to have had an event at with an exposure time of $t_i + \Delta_i$. If $t_i + \Delta_i > 9$ then subject i is considered not to have event at with an exposure time of 9 months.
5. Steps 2-4 will result in a full dataset with no missing primary endpoint data over the period (0-9] months.

6. This full dataset is then analysed in the same manner as described for the primary endpoint using the Cochran-Mantel-Haenszel approach and the treatment effect and associated SE are estimated.
7. Steps 2-6 are repeated multiple times and the resulting treatment effect estimates and SEs are combined in SAS via PROC MIANALYZE using Rubin's rules. This will provide the estimated treatment effect having imputed missing data under a missing at random assumption.

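### Every route into the mITT set depends on events after randomisation, and no planned efficacy analysis on the ITT set would check the effect

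*SAP*

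**What the plan says.** The SAP Introduction proposes a combined primary analysis on a "modified ITT analysis set defined by the eligibility of dosing with IMP as intended in the clinical study protocol". Section 3.1 then gives the rule: the mITT set "includes patients that fulfil at least one of the following criteria".

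- Criterion 1: randomised before 1 December 2019, and the patient "had at least one post-baseline assessment for efficacy".
- Criterion 2: the 3-month assessment visit took place before 1 March 2020.
- Criterion 3: "the patient received the 6th cycle of IMP", with the added condition that this was after 1 March 2020.

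Section 2.5 says that mITT replaces the Full Analysis Set. Section 5 says that, unless otherwise stated, "all efficacy variables will be analysed using the MITT analysis set", and no later efficacy section states otherwise. Section 3.1 also defines an ITT set of all randomised patients, but no efficacy analysis is assigned to it. Section 5.2 lists three ways of handling a missing primary endpoint (observed cases, missing counted as an event, tipping point) and names no other analysis set.

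**The concern.** Eligibility for dosing is a calendar matter: whether the randomisation date left enough time before the hold. It is settled at randomisation and cannot differ by arm except by chance. Whether a patient attended an assessment, reached the 3-month visit or received a 6th infusion is known only later and may depend on the treatment. The Introduction says that the program was closed because of "an accumulation of severe allergic reactions, primarily observed after repeated dosing", so drug-driven stopping is more than a theoretical possibility.

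If membership of the set depends on treatment, the two arms within it are no longer protected by randomisation. A planned analysis on all randomised patients would show whether that matters. None is planned.

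**Working it through.** **1. The SAP's own counts (Table 1).** The totals reproduce: 301 + 290 = 591 randomised, 297 + 285 = 582 dosed, 257 + 194 = 451 with at least 6 IMP cycles. From these:

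- never dosed: (301 − 297) + (290 − 285) = 4 + 5 = 9
- dosed, fewer than 6 cycles: (297 − 257) + (285 − 194) = 40 + 91 = 131, and 131/582 = 22.5%

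The 131 is a ceiling on early stopping. It includes patients cut off by the hold, patients in the 2 µmol/kg arm (outside the primary comparison) and patients who stay in mITT through criterion 1. The SAP gives no mITT size and no exclusions by arm.

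**2. What each criterion rests on.**

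| Criterion | Fixed at randomisation | Known only afterwards |
|---|---|---|
| 1 | date before 1 December 2019 | an efficacy assessment exists |
| 2 | nothing | the 3-month visit took place before 1 March 2020 |
| 3 | nothing | the 6th IMP cycle was received |

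**3. Who can be lost.**

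- *Randomised before 1 December 2019.* One assessment keeps the patient in. Only those with none are lost under criterion 1. They have no month-9 value, so the observed-case estimate does not change. The missing-as-event and tipping-point analyses never reach them.
- *Randomised from 1 December 2019.* From 1 December to 1 March is 91 days, so criterion 2 is almost out of reach and entry rests on criterion 3. Its date is a problem, because the Introduction puts dosing on hold on 1 March 2020. Assume 14-day cycles: cycle 6 falls 5 × 14 = 70 days after cycle 1. A first dose on 1 December 2019 gives cycle 6 on 9 February 2020, and 1 March 2020 minus 70 days is 22 December 2019. A patient starting between 1 and about 21 December, dosed on schedule, therefore has six cycles before 1 March and can fail all three criteria.

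**4. Possible size, on assumed figures.** The comparison has about 301 + (2/3) × 290 = 494 patients, or 247 per arm. Assume no treatment effect, a 40% risk in both arms, and a fraction f of the active arm only excluded, with CIPN risk r. The retained active risk is (0.40 − f·r)/(1 − f). Rejection is a normal approximation for two simple proportions at two-sided 0.05, not the exposure-weighted estimator.

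| f | r | Apparent risk ratio | Two-sided rejection |
|---|---|---|---|
| any of the below | 40% | 1.00 | 5.0% |
| 2% | 60% to 100% | 0.99 to 0.97 | 5.1% to 5.9% |
| 5% | 60% to 100% | 0.97 to 0.92 | 5.6% to 11.0% |
| 10% | 60% to 100% | 0.94 to 0.83 | 7.8% to 32.4% |

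The sign can reverse: with f = 5% and r = 20%, (0.40 − 0.01)/0.95 = 0.4105, a ratio of 1.03.

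**5. Effect on the missing-as-event analysis.** Assume 150 per arm, a true risk of 40% in both, and 9 active (6%) and 3 placebo (2%) patients with no assessment. Kept and counted as events: (0.40 × 141 + 9)/150 = 43.6% against (0.40 × 147 + 3)/150 = 41.2%, ratio 1.06. Excluded: 40% against 40%, ratio 1.00. Here 1.00 is the true value. The example shows a worst-case penalty that is no longer applied, not a bias in the estimate.

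**The case against.** Much can be said for the plan.

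- The Introduction is a summary that promises detail later, and Section 3.1 supplies it. The Full Analysis Set that mITT replaces is defined in the protocol, which is not at hand, so the assessment clause cannot be called new.
- Membership is agreed before unblinding, exclusion reasons are listed per patient (Section 3.1), and mITT numbers are tabulated by treatment group (Section 4.1).
- The allergy mechanism fits criterion 1 poorly. The reactions came mainly after repeated dosing, while cold sensitivity is summarised from cycle 2 (Section 5.3.2) and CIPN at treatment visits (Section 5.1.1). A patient who reacts after several doses should already have an assessment and stay in.
- Read literally, criterion 3 may admit few or no patients from either arm, so selection through it is not shown to occur.
- An all-randomised analysis brings in patients with no first dose, from which month 9 is counted, and perhaps no oxaliplatin, so that the log offset is undefined.

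All of this limits the size of the point. It does not remove it. Blinding and agreement before unblinding prevent selection by the analyst, not selection by the drug. Listings and counts show that exclusions differ; they do not show what the difference does to the estimate. The never-dosed patients need a rule, which can be written.

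**Conclusion.** The point holds as a mismatch between the stated basis of the mITT set and its definition, with no planned efficacy analysis outside that set. Differential selection is possible, mainly for patients randomised from 1 December 2019; the loss through the criterion 1 clause may be small.

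Three stronger readings are tempting and not supported:

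- *That the set favours PledOx.* This needs excluded active patients to carry a higher CIPN risk than those retained. The SAP does not say so; equal risk gives no bias and lower risk reverses the sign.
- *That 22.5% of patients are removed.* The 131 of 582 bounds early stopping and is not a count of exclusions.
- *That patients who stop early for toxicity generally leave the primary comparison.* Anyone randomised before 1 December 2019 with one assessment remains, analysed as randomised.

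The ranges in the working rest on assumed exclusion fractions and risks and on simple proportions; they show what could happen, not what did.

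**What to change.** 1. In Section 3.1, define the date-based part of mITT by randomisation date alone and delete the post-baseline-assessment clause, so that Section 5.2 handles patients without data.
2. At minimum, repeat the primary analysis, with the Section 5.2 imputations, on all randomised patients as a sensitivity analysis. If criteria 2 and 3 stay, this is the only check on them.
3. State a rule for the 9 never-dosed patients. Examples: restrict to patients with at least one IMP dose, or count month 9 from randomisation and use an unweighted proportion where oxaliplatin exposure is zero.
4. Summarise mITT exclusions by arm and reason, in addition to the planned listing.
5. Reconcile the date in criterion 3 with the hold on dosing from 1 March 2020 in the Introduction.

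The cost is SAP wording before unblinding, one extra run of the primary table and a few more missing month-9 values under item 1. Item 2 may add more. The Introduction targets a data cut-off in the third quarter of 2020, and a patient first dosed in January 2020 reaches month 9 in October 2020. Such administrative gaps should be reported separately from dropout when the missing-as-event result is read.
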